6.4.3 Prohibited concomitant therapy

Anti-neoplastic therapies

Treatment with systemic anticancer agents (chemotherapy, hormone therapy, targeted or biologic agents) other than the protocol treatment is not permitted until disease progression is documented per RECIST. Palliative radiotherapy or surgery may be allowed and should be discussed with Novartis prior to administration.

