14.1.25 Definition of start and end dates for time to event variables

Assessment date

For each assessment (i.e. evaluation number), the **assessment date** is calculated as the latest of all measurement dates (e.g. X-ray, CT-scan) if the overall lesion response at that assessment is CR/PR/SD/UNK. Otherwise - if overall lesion response is progression - the assessment date is calculated as the earliest date of all measurement dates at that evaluation number.

Start dates

For all “time to event” variables, other than duration of response, the randomization/ date of treatment start will be used as the start date.

For the calculation of duration of response the following start date should be used:

- Date of first documented response is the assessment date of the first overall lesion response of CR (for duration of overall complete response) or CR / PR (for duration of overall response) respectively, when this status is later confirmed.

End dates

The end dates which are used to calculate ‘time to event’ variables are defined as follows:

- Date of death (during treatment as recorded on the treatment completion page or during follow-up as recorded on the study evaluation completion page or the survival follow-up page).
- Date of progression is the first assessment date at which the overall lesion response was recorded as progressive disease.
- Date of last adequate tumor assessment is the date the last tumor assessment with overall lesion response of CR, PR or SD which was made before an event or a censoring reason occurred. In this case the last tumor evaluation date at that assessment is used. If no post-baseline assessments are available (before an event or a censoring reason occurred) the date of randomization/start of treatment is used.
- Date of next scheduled assessment is the date of the last adequate tumor assessment plus the protocol specified time interval for assessments. This date may be used if back-dating is considered when the event occurred beyond the acceptable time window for the next tumor assessment as per protocol (see [Section 14.1.26](#)).

Example (if protocol defined schedule of assessments is 3 months): tumor assessments at baseline - 3 months - 6 months - missing - missing - PD. Date of next scheduled assessment would then correspond to 9 months.

- Date of discontinuation is the date of the end of treatment visit.

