5.5.2 Progression-Free Survival (PFS)

Progression-free survival is defined as time from the start of study treatment to progression of disease (PD) or death due to any cause (whichever occurs first).

Time to progression of disease is defined as the time when progression is first observed:

- At least a 20% increase in the sum of diameter of all measured target lesions, taking as reference the smallest sum of diameter of all target lesions recorded at or after baseline. In addition to the relative increase of 20%, the sum must also demonstrate an absolute increase of 5 mm;

Or

- Unequivocal progression of existing non-target lesions;

Or

- Emergence of new lesions.

The calculation of PFS was based on the date of the imaging examination, not the date of the RECIST tumor evaluation or the date of the visit.

For calculation of PFS, if imaging examinations were completed on multiple dates, the progression date or censored date was determined according to the following rules:

- For patients with progression of disease, the date of progression is defined as the earliest date when it is assessed that there is progression.
- For patients without progression of disease, the censored date is defined as the date of the latest imaging examination within the visit.

If the patient was alive and progression-free at the time of data cutoff, the date of the last imaging examination of the measurable lesion was used as the date of the last evaluation in the PFS analysis, i.e., the censored date. If the patient had no PFS data available or was missing baseline data assessment and was still alive at the data cutoff, the study treatment start date was used as the censored date in the PFS analysis. Detailed censoring rules for PFS are shown in Table 2.

Table 2 Censoring rules for PFS

#	Situation	Progression or censored date	Result
1	No baseline or post-baseline tumor assessment	Study treatment start date	Censored
2	Documented progression of disease	Progression date	Progression
3	No progression based on RECIST assessment (i.e. clinical progression based on investigator's assessment) leading to end of treatment	Date of discontinuation of treatment	Progression
4	No events occurred	Date of last adequate tumor assessment	Censored
5	Initiation of new anti-cancer therapy	Date of last adequate tumor assessment prior to initiation of subsequent anticancer therapy (start date of the	Censored

		study treatment if there is no post-baseline imaging examination)	

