6	Death ^a	Date of death	Progression
7	Event ^b documented after two or more missing tumor assessments	Date of last adequate tumor assessment prior to two or more consecutive tumor assessments not performed as per protocol	Censored

Note 1: Adequate assessment included tumor assessment in the following situations: CR, PR, SD, PD
Note 2: ^a Including cases where no tumor evaluation was conducted after enrollment and death occurred during two consecutive scheduled tumor evaluation visits (i.e., date of death is less than or equal to 24 weeks + 2 weeks from the start date of study treatment).
Note 3: ^b Indicating that the date of death or progression of disease is greater than 24 weeks + 2 weeks from the last tumor assessment.

New anticancer therapy is defined as the following drugs received at or after the start of study treatment:

- The name of the drug is Capecitabine, Temozolomide, or Sandostatin LAR
- Indication or reason for administration is chemotherapy or anti-tumor

Baseline is defined as the last RECIST1.1 assessment prior to the start of study treatment.

PFS was analyzed using statistical methods similar to those used for OS analysis.

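### SAP Table 2 gives opposite PFS results for a patient with both new anticancer therapy and progression or death, and states no order of precedence

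*SAP*

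**What the plan says.** SAP 5.5.2 defines PFS as the time from start of treatment to the first of progression or death. Table 2 then lists seven situations. Those that matter here are:

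- Row 2, "Documented progression of disease": an event on the progression date.
- Row 5, "Initiation of new anti-cancer therapy": censored at the "Date of last adequate tumor assessment prior to initiation of subsequent anticancer therapy", or at treatment start if there is no post-baseline imaging.
- Row 6, death: an event on the date of death.

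Note 1 to the table reads: "Adequate assessment included tumor assessment in the following situations: CR, PR, SD, PD". Below the table the SAP adds: "New anticancer therapy is defined as the following drugs received at or after the start of study treatment". Three drugs are named, together with any drug given as chemotherapy or for an anti-tumor indication. Neither row 5 nor this definition refers to progression.

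In the protocol, section 14.1.25 defines the date of last adequate assessment by "the last tumor assessment with overall lesion response of CR, PR or SD which was made before an event" or a censoring reason. Section 14.1.19 censors PFS only for a patient without an event. Table 14-5, situation F, option 1 gives censoring at the last adequate assessment as the default for new anticancer therapy, and section 14.1.27 asks that this situation be specified in detail. Section 6.4.3 says that systemic anticancer treatment "other than the protocol treatment is not permitted until disease progression is documented per RECIST". SAP section 7 declares no change from the protocol's analysis.

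**The concern.** A patient can meet row 5 and also row 2 or row 6. The rows then assign opposite status, and sometimes different dates, and nothing in the SAP says which governs. The SAP's first-of rule ranks progression against death only; it does not place new therapy in that order.

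Protocol 6.4.3 makes therapy after progression the sequence a compliant patient follows, so the overlap is foreseeable. Version 3.2 of the SAP revised row 5's censoring date and added the definition of new therapy, but set no order.

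PFS is one of two named efficacy endpoints in a study done to supply Chinese efficacy data to the regulator. Two programmers following Table 2 faithfully could report different event counts and medians from the same data.

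**Working it through.** **1. Test records.** Days 169 and 253 are the scheduled week 24 and week 36 assessments in SAP 5.1.1. The records are hypothetical.

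| Record | Rows 2 and 6 | Row 5 as written |
|---|---|---|
| A: SD day 169, PD day 253, capecitabine day 270 | Event, day 253 | Censored, day 253 (PD adequate under Note 1) |
| B: SD day 169, qualifying drug day 180, PD day 253 | Event, day 253 | Censored, day 169 |
| C: SD day 169, qualifying drug day 180, death day 260 | Event, day 260 | Censored, day 169 |

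Row 7 (two or more missed assessments) does not apply. The gaps from the last assessment before the event are 253 − 169 = 84 days and 260 − 169 = 91 days, below the 26 × 7 = 182 days in Note 3.

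**2. Can a fixed ranking of rows repair this?**

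- Rows 2 and 6 always first: A is an event, as the PFS definition requires. B and C become events after new therapy, against the protocol default, and row 5 is idle for everyone who later progresses or dies.
- Row 5 always first: B and C follow the protocol default, but A loses a documented progression.
- Earliest occurrence decides: A is an event on day 253; B and C are censored at day 169. All three agree with the PFS definition, protocol 14.1.19 and the situation F default.

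Only the time-ordered rule handles all three.

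**3. Note 1.** Adequate assessments set censoring dates in rows 4, 5 and 7. A patient whose last adequate assessment is PD already has a row 2 event, so listing PD serves no purpose in a censoring date. Under the protocol's definition, row 5 read literally would censor A at day 169. Deleting PD from Note 1 is therefore not enough without rewording row 5.

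**4. Size for record A, if row 5 overrode row 2.** The documents give no PFS target or event count to reproduce. Inputs:

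- n = 60 (planned sample size).
- Median 11.04 months (everolimus arm of the phase III pNET trial, protocol 1.2.1.2), for illustration.
- Exponential PFS (assumed).
- q, the share of events recoded as censored at the same time, unrelated to event time (assumed; not in the documents).

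Recoding lowers the apparent hazard from λ to (1 − q)λ, so apparent median = 11.04 / (1 − q). Simulating 60 patients with 12-weekly scans and an assumed uniform 24 to 60 months of follow-up gives about 54 events before recoding.

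| q | Apparent median (months) | Events left |
|---|---|---|
| 0 | 11.04 | 54 |
| 10% | 11.04 / 0.9 = 12.3 | 54 × 0.9 ≈ 49 |
| 30% | 11.04 / 0.7 = 15.8 | 54 × 0.7 ≈ 38 |
| 50% | 11.04 / 0.5 = 22.1 | 54 × 0.5 = 27 |

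If row 2 prevails, the effect is zero. Records B and C were not quantified.

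**The case against.** The strongest reply is that context settles record A. Row 2 makes documented progression an event; PFS runs to the first of progression or death; the SAP's dating rule gives a censored date to patients without progression; and protocol 14.1.19 censors only patients without an event. This stands. A reader might infer that the SAP actually censors every patient who progresses and then starts next-line therapy. The documents do not support that: it is row 5 read alone. But the same context does not settle B and C, where general event precedence contradicts row 5 and the protocol default.

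A second reply is that Note 1 may only be meant to exclude unevaluable scans, since UNK is the category left out. That is a plausible purpose, but it does not require PD on the list, and the departure from protocol 14.1.25 remains.

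A third concerns how often this arises. From protocol 6.4.3 a reader might infer that row 5 mainly catches patients who have already progressed. That is not established. Protocol 6.4 asks for medications until the last dose, Table 7-1 marks them only through end of treatment, and section 7.1.7 extends the form to 30 days after. Section 6.4.1 speaks more broadly of drugs given during the study, so some later therapy may be recorded, but q may be small.

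Finally, a simulation on the scan schedule can suggest that q = 10% lengthens the median by 25%. That jump is an artefact. With months of 365.25 / 12 = 30.4375 days, 4 × 84 days = 11.04 months, exactly the assumed median, and 5 × 84 days = 13.80. The typical gridded median therefore moves one whole scan interval. The smooth figure is 12.3 / 11.04, about 11%.

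**Conclusion.** Table 2 is wrong as written: it gives two contradictory results for any patient with both new anticancer therapy and progression or death, and no fixed ranking of its rows resolves them. For progression followed by therapy, the PFS definition and protocol 14.1.19 support an event. For therapy followed by progression or death, row 5 and the protocol default support censoring. Note 1 departs from protocol 14.1.25 while SAP section 7 reports no departure.

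This is a conflict in the rules, not a demonstrated bias in the reported PFS. The medians of 12.3, 15.8 and 22.1 months hold only if row 5 overrides row 2, PFS is exponential, and the recoded share is 10%, 30% or 50%; the true share is unknown. PFS is secondary and descriptive in a single-arm study whose sample size rests on feasibility, so no alpha or power is affected. The change should still be made, because the ambiguity can alter a reported efficacy result.

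**What to change.** Three wording changes in SAP 5.5.2:

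1. Limit row 5 to new anticancer therapy started before documented progression or death.
2. Remove PD from Note 1 and restore the protocol 14.1.25 definition: CR, PR or SD, before an event or a censoring reason.
3. State that the earliest event or censoring reason decides the row. Progression before new therapy is then an event under row 2, and progression or death after new therapy is censored under row 5. The same line settles clinical progression under row 3 followed by a new drug.

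Then run the PFS program against records A, B and C. The expected results are an event on day 253, censored at day 169, and censored at day 169. The cost is a SAP revision and a program check; no new data are needed.

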7.2 Assessment types

7.2.1 Efficacy assessments

Tumor assessments are to be performed for screening purposes and are needed to determine the eligibility of the patient. Last available results of scans performed within 28 days prior to first dose of study drug will be used as baseline values. Negative scans at screening need not be repeated unless warranted by signs and symptoms suggesting disease progression. The assessment data will be collected until disease progression, unacceptable toxicity, death, protocol deviation or other reason that may leads to discontinuation or the end of study.

The following tumor assessments are to be performed and assessed prior to enrollment:

- Abdominal and pelvic triphasic CT or multiphase MRI;
- Chest X-ray (and/or chest CT if disease is present in chest).

To determine eligibility, measurable and non-measurable lesions must be assessed and target lesions identified prior to enrollment. For definition of measurable and target lesions please refer to RECIST 1.1 ([Appendix 1](#))

The same method of assessment and the same technique should be used to characterize each identified and reported lesion at baseline and after every 12 weeks while on-study. All radiology evaluations will be performed initially by the local radiologist.

Details of response assessment are provided in full protocol based on RECIST1.1, and are based exclusively on radiological findings obtained at tumor assessments.

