².=After the last adequate tumor assessment. "Date of next scheduled assessment" is defined in Section 14.1.25.

³.=The rare exception to this is if the patient dies no later than the time of the second scheduled assessment as defined in the protocol in which case this is a PFS event at the date of death.

The primary analysis and the sensitivity analyses must be specified in the protocol. Clearly define if and why options (1) are not used for situations C, E and (if applicable) F.

Situations C (C1 and C2): Progression or death after one or more missing assessments: The primary analysis is usually using options (1) for situations C1 and C2, i.e.

- (C1) taking the actual progression or death date, in the case of only one missing assessment.
- (C2) censoring at the date of the last adequate assessment, in the case of two or more consecutive missing assessments.

In the case of two or missing assessments (situation C2), option (3) may be considered jointly with option (1) in situation C1 as sensitivity analysis. A variant of this sensitivity analysis consists of backdating the date of event to the next scheduled assessment as proposed with option (2) in situations C1 and C2.

Situation E: Treatment discontinuation due to ‘Disease progression’ without documented progression: By default, option (1) is used for situation E as patients without documented PD should be followed for progression after discontinuation of treatment. However, option (2) may be used as sensitivity analysis. If progression is claimed based on clinical deterioration instead of tumor assessment by e.g. CT-scan, option (2) may be used for indications with high early progression rate or difficulties to assess the tumor due to clinical deterioration.

Situation F: New cancer therapy given: the handling of this situation must be specified in detail in the protocol. However, option (1), i.e. censoring at last adequate assessment may be used as a default in this case.

Additional suggestions for sensitivity analyses

Other suggestions for additional sensitivity analyses may include analyses to check for potential bias in follow-up schedules for tumor assessments, e.g. by assigning the dates for censoring and events only at scheduled visit dates. The latter could be handled by replacing in [Table 14-5](#) the “Date of last adequate assessment” by the “Date of previous scheduled assessment (from baseline)”, with the following definition:

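### SAP Table 2, Note 3: the 26-week limit has no stated start date when the only earlier scan is baseline, so it can clash with row 7's own label, protocol option C1 and Note 2

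*SAP*

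**What the plan says.** SAP 5.5.2, Table 2 sets the PFS event and censoring rules.

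- **Row 2** makes documented progression an event on its date.
- **Row 6 with Note 2** makes death an event. It covers patients with no scan after enrolment ("Including cases where no tumor evaluation was conducted after enrollment and death occurred during two consecutive scheduled tumor evaluation visits"), and the limit is that the "date of death is less than or equal to 24 weeks + 2 weeks from the start date of study treatment".
- **Row 7** censors an event "documented after two or more missing tumor assessments". Its date column also refers to at least two consecutive scans not done, and censors at the last adequate assessment before them.
- **Note 3**, attached to the word for the event in row 7, is the row's only numeric definition: "date of death or progression of disease is greater than 24 weeks + 2 weeks from the last tumor assessment".
- **Note 1** counts an assessment as adequate only if it is rated CR, PR, SD or PD.

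The SAP's wording lets baseline count as a tumour assessment. Row 1 is labelled "No baseline or post-baseline tumor assessment", and "Baseline is defined as the last RECIST1.1 assessment prior to the start of study treatment". Protocol 7.2.1 sets its timing: "Last available results of scans performed within 28 days prior to first dose of study drug will be used as baseline values". On-treatment scans are due every 12 weeks, plus or minus 1 week (Protocol Table 7-1; SAP Appendix 1).

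For exactly one missed scan (situation C1), Protocol 14.1.27 describes the usual primary analysis as "taking the actual progression or death date, in the case of only one missing assessment".

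**The concern.** Notes 2 and 3 use the same 26 weeks but count them from different dates: treatment start in Note 2, the last scan in Note 3. For a patient with no scan since baseline, the two starting points can differ by up to 28 days. Note 3's two-week allowance matches the visit windows but does not cover that lag.

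Two things follow if Note 3 is programmed as worded. A progression found on schedule at Week 24 after one missed scan can be handled as if two scans had been missed. A death late in Note 2's window meets two notes that give opposite results.

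The censoring date adds to the problem. A baseline scan carries no CR, PR, SD or PD rating, so such a patient has no adequate assessment to fall back on. Row 5 names treatment start for this situation; row 7 does not. Protocol 14.1.25 and 14.1.34 would supply treatment start, which leaves one day of follow-up. The records at risk are early failures, so any error lengthens PFS.

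**Working it through.** **Inputs**
- Limit in Notes 2 and 3: 26 × 7 = 182 days.
- Week 24 scan: 168 days after first dose, ± 7 days (Protocol Table 7-1).
- Baseline lag x: 0 to 28 days before first dose (Protocol 7.2.1).

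**1. The plan's limit.** Two 12-week intervals plus a one-week window at each end give 168 + 7 + 7 = 182 days. Between post-baseline scans, one missed scan gives a gap of at most 182 days, which is not over the limit. Two missed scans give at least 252 − 14 = 238 days. There the limit separates one miss from two correctly.

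**2. Week 12 missed, progression at Week 24, clock starting at baseline.** Gap = days from first dose + x. Note 3 is met when the gap exceeds 182.

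| Week 24 scan | Days from first dose | Note 3 met if x is at least | Gap at x = 28 |
|---|---|---|---|
| 7 days early | 161 | 22 | 189 |
| nominal | 168 | 15 | 196 |
| 7 days late | 175 | 8 | 203 |

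Counting days with +1 lowers each threshold by one day. Over 15 in-window scan days and 29 possible lags there are 435 combinations. For a scan d days after first dose, d − 154 lags exceed the limit. That runs from 7 to 21, averages 14, and totals 15 × 14 = 210, or 48%. This is a share of date combinations. It is a share of patients only if lags and scan days are spread evenly, which the documents do not show.

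**3. Deaths with no scan since baseline, t days after first dose.** Note 2 gives an event if t ≤ 182. Note 3 applies if t + x > 182. Both hold for t from 183 − x to 182:
- x = 28: days 155 to 182
- x = 14: days 169 to 182
- x = 0: none

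**4. Size, illustrative.** Assume that 5 to 15% of 60 patients (3 to 9) miss Week 12. Take exponential PFS with the phase II medians in Protocol 1.2.1.2, 16.7 and 9.7 months, and 168 days = 5.52 months. The chance of an event by Week 24 is 1 − exp(−0.693 × 5.52 / median), which is 0.20 and 0.33. Expected patients meeting Note 3: 3 × 0.20 × 0.48 = 0.3, up to 9 × 0.33 × 0.48 = 1.4. These figures are probably too high, because 0.20 to 0.33 covers any PFS event by Week 24, not only progression first seen at that scan.

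One such patient censored at Day 1 leaves the risk set. With no other censoring, 6-month PFS moves from 48/60 = 80.0% to 48/59 = 81.4%, or from 40/60 = 66.7% to 40/59 = 67.8%. That is 1.1 to 1.4 points per patient.

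**5. With the clock at first dose.** The Week 24 gap is 161, 168 or 175 days, never over 182, so progression stays an event. Notes 2 and 3 overlap on 0 days. Progression at Week 36 after two missed scans has a gap of at least 252 − 7 = 245 days and is still censored.

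**The case against.** The strongest reply is that row 7 does not reach the one-miss case at all. Its label and its date column both require at least two missed scans, so row 2 applies and the progression counts. Note 3 can be read as adding a time condition to that requirement, not replacing it. Protocol option C1 agrees, and SAP section 7 declares no change from the protocol's methods. Protocol 14.1.25 also substitutes treatment start when there is no post-baseline scan, and the same could be assumed for Note 3's clock. For deaths, Note 2 is the more specific rule.

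Much of this stands. A reader might infer that the plan censors these progressions outright, or that every patient with a baseline lag over 14 days is wrongly censored. The documents do not support that: it is the outcome of coding Note 3 alone and ignoring the rest of its row. A reader might also infer that deaths counted by Note 2 are censored. The SAP does not say so; Note 2 expressly makes them events, and what remains is a conflict without a stated precedence.

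The reply does not remove the gap. Note 3 is the only number in row 7 and is what a programmer would naturally code. It omits the word that would limit it to adequate assessments and does not cite 14.1.25. If it is taken to mean post-baseline scans only, it has no starting date for these patients, and the same clarification is needed.

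**Conclusion.** The point holds as a defect of definition. Note 3 does not state its starting date for a patient whose only earlier scan is baseline. Read literally, it disagrees with row 7's label, row 2 and option C1 after one missed scan. For deaths, it overlaps Note 2 in at most the last 28 days of the 26-week window.

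The arithmetic needs only the documents' dates. The patient count does not: it rests on an assumed rate of missed Week 12 scans, evenly spread baseline lags and exponential PFS. On those assumptions about one patient or none is affected. PFS is a secondary endpoint, described by Kaplan-Meier without a hypothesis test, so no formal conclusion depends on this. It is still worth correcting: the direction is one-sided, 6-month probabilities are planned (SAP 5.5.1, applied to PFS in 5.5.2), and two notes to one table should not classify the same death differently.

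**What to change.** Reword Note 3 so that its 26 weeks run from whichever is later: the start of study treatment or the last post-baseline tumour assessment. This matches Note 2 and the scan schedule, keeps a Week 24 progression after one missed scan as an event, and removes the overlap for deaths.

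In row 7, add the fallback that row 5 already has: if there is no adequate post-baseline assessment, censor at the study treatment start date.

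The cost is one sentence in Note 3, one phrase in row 7 and about one line of code. The only downside is that PFS may come out slightly less favourable than under a literal coding of Note 3.

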- Date of last contact is defined as the last date the patient was known to be alive. This corresponds to the latest date for either the visit date, lab sample date or tumor assessment date. If available, the last known date patient alive from the survival follow-up page is used. If no survival follow-up is available, the date of discontinuation is used as last contact date.

- Date of secondary anti-cancer therapy is defined as the start date of any additional (secondary) antineoplastic therapy or surgery.

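### Imputed medication start dates can make a drug look newly begun on day 1 and censor PFS at treatment start (SAP 5.3.5 with 5.5.2); the definition of new therapy also omits surgery

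*SAP*

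**What the plan says.** **Trigger.** Row 5 of Table 2 in SAP 5.5.2 applies on "Initiation of new anti-cancer therapy". It censors PFS at the last adequate tumor assessment before that therapy. The fallback is the start of "study treatment if there is no post-baseline imaging examination".

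**Definition.** Below Table 2 the SAP states: "New anticancer therapy is defined as the following drugs received at or after the start of study treatment". Two bullets follow without a connecting word: "The name of the drug is Capecitabine, Temozolomide, or Sandostatin LAR" and "Indication or reason for administration is chemotherapy or anti-tumor".

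**Start dates.** SAP 5.3.5 uses the first-dose date as a medication's start date in three cases:
- everything is missing;
- only the year is known and it is the year of first dose;
- year and month are known and both match the first dose.

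Other partial dates go to the first day of the known month or to 1 January of the known year. If timing relative to first dose cannot be determined, the drug is treated as concomitant.

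**Protocol.** Section 14.1.25 reads: "Date of secondary anti-cancer therapy is defined as the start date of any additional (secondary) antineoplastic therapy or surgery". On the last adequate assessment the same section adds: "If no post-baseline assessments are available (before an event or a censoring reason occurred) the date of randomization/start of treatment is used". For new therapy, 14.1.27 says that "censoring at last adequate assessment may be used as a default in this case". Section 6.4.3 says that palliative radiotherapy or surgery may be allowed, after discussion with the sponsor. Section 6.4.1 provides a CRF page for procedures and non-drug therapies. SAP Section 7, which would list changes from the protocol's planned analysis, says there are none.

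**The concern.** The 5.3.5 imputation is reasonable for sorting drugs into prior and concomitant, where the first-dose date is a cautious choice. It is not cautious when the same date feeds a censoring rule, because first dose is the earliest date that the definition accepts as new therapy. A patient caught this way loses all PFS follow-up. A documented progression may be lost too, because Table 2 does not say whether row 2 (progression) or row 5 (new therapy) prevails.

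The situation is plausible here. Sandostatin LAR is named outright. Protocol 1.1 describes somatostatin analogues as the standard symptomatic treatment in this disease. The exclusion criteria do not list them, and protocol 6.4 has drugs taken in the 30 days before treatment recorded on the CRF. Long-standing drugs are the ones most likely to have an incomplete start date.

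The second issue runs the other way. A patient who has anti-tumor surgery before progression stays uncensored under the SAP, so scans after surgery count toward everolimus PFS.

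**Working it through.** **Step 1: the chain on day 1.** Table 2's note defines an adequate assessment as one with a response category (CR, PR, SD or PD). A baseline scan has none, so no adequate assessment precedes a therapy dated to day 1. Row 5's fallback is worded for patients without post-baseline imaging. For a patient with later scans, protocol 14.1.25 supplies treatment start. Protocol 14.1.34 computes time as end date minus start date plus 1, so PFS is 1 day, censored.

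**Step 2: worked dates.** Assume a first dose on 10 January 2017 and scans every 84 days, on days 85, 169, 253 and 337.

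| Recorded start of new therapy | Date used | PFS censored at |
|---|---|---|
| 20 December 2017, complete | 20 December 2017 | day 337 |
| December 2017, day missing | 1 December 2017 | day 253 |
| January 2017, day missing | 10 January 2017 | day 1 |
| 2017 only | 10 January 2017 | day 1 |
| all missing | 10 January 2017 | day 1 |
| 2018 only | 1 January 2018 | day 337 |

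A therapy truly begun on 20 December 2017 but dated only by year loses 337 − 1 = 336 days. A drug begun before entry with no date, or with only the year 2017, also lands on day 1. One begun in a known earlier year does not, because it is imputed to before first dose.

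**Step 3: size.** The plan gives no figure to reproduce, so the inputs are assumptions.
- N = 60 (planned).
- Share of Sandostatin LAR users p = 45/(115 + 45) = 0.281. This is the octreotide LAR stratum of a phase II study in protocol 1.2.1.2, not a prevalence for this trial.
- Median PFS 16.7 months in users and 9.7 in non-users, from the same non-randomised strata.
- Fraction f of users dated to day 1: 10% to 20%, with no source in the documents.

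The model is S(t) = (1 − w)·exp(−ln2·t/9.7) + w·exp(−ln2·t/16.7). With 60pf patients removed on day 1, the users' share becomes w = p(1 − f)/(1 − pf).

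| p | f | Patients removed | Median (months) | Shift (months) | 12-month PFS |
|---|---|---|---|---|---|
| 0.281 | 0 | 0 | 11.18 | – | 0.476 |
| 0.281 | 0.10 | 1.7 | 11.06 | 0.12 | 0.472 |
| 0.281 | 0.20 | 3.4 | 10.94 | 0.25 | 0.468 |
| 0.281 | 1 | 16.9 | 9.70 | 1.48 | 0.424 |

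At p = 0.10 the shifts are 0.05 and 0.09 months for f = 0.10 and 0.20. The f = 1 row is an extreme bound. At p = 0.281 the standard error rises by 1/√(1 − pf), that is 1.014 to 1.029, if events fall in proportion to patients.

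For scale, an exponential approximation to the 95% interval is 11.18·exp(±1.96/√d). With d = 40 events it is 8.2 to 15.2 months (width 7.0). With d = 60 it is 8.7 to 14.4 (width 5.7).

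The direction is not fixed. A simulation with N = 60, an assumed exponential median of 11.04 months (the phase III value in protocol 1.2.1.2) and 4,000 runs gave a mean Kaplan-Meier median of 10.87 with nobody misdated. With three patients misdated it gave 10.37 if all came from the longer-PFS half and 11.97 if all came from the shorter half. A random three gave 11.14, so part of these differences is only the step form of a Kaplan-Meier median at small N. The one-sided draws are stress cases.

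**Step 4: surgery and radiotherapy.** The SAP definition is limited to drugs. Protocol 14.1.25 covers any additional antineoplastic therapy, and surgery. Radiotherapy given as antineoplastic treatment also falls outside the SAP wording, and neither document says how palliative radiotherapy counts. The documents do not allow the effect to be quantified.

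**The case against.** **An ongoing drug is not newly initiated.** Read alone, the phrase about drugs received at or after treatment start might suggest that every patient continuing Sandostatin LAR is censored on day 1. The documents do not support that. Row 5 speaks of initiation, and 5.3.5 treats drugs begun earlier and continued as a recognised class. The exposure is confined to incomplete dates.

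**Incomplete dates should be few.** Protocol 9.4 sends queries for missing values, and 11.6 requires missing data to be explained. Section 6.4.3 bars other systemic anticancer agents, hormone therapy included, until RECIST progression. The SAP also does not expressly say that 5.3.5 dates feed Table 2. All this lowers the likely count. It does not remove the gap, because symptomatic use remains possible and 5.5.2 gives no other date rule for these drugs.

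**The censoring date is not undefined.** Row 5's fallback misses patients with later scans, but protocol 14.1.25 fills that hole. Row 5's date also matches the protocol default in 14.1.27 and is not in dispute.

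**The SAP may narrow the definition.** A reader might call the drug-only wording a breach of the protocol. Section 14.1.25 belongs to a general guideline appendix, and 14.1.28 and 14.1.29 leave study-specific choices to the protocol or analysis plan. The narrowing may therefore be legitimate. What stands is that 14.1.29 wants departures defined in the analysis plan, while SAP Section 7 reports none.

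**The missing connector is editorial.** Joining the two bullets by OR is the natural reading. AND would miss anti-tumor drugs outside the three names, but little supports that reading.

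**Conclusion.** The point holds as a minor correction. Followed as written, SAP 5.3.5 and 5.5.2 can turn an incomplete start date into day-1 censoring and discard a patient's PFS record. The definition also leaves out surgery without saying so.

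The documents do not show that any patient is affected. With 2 to 3 misdated patients, a shift of about 0.1 to 0.25 months rests on a borrowed user share, borrowed medians and an assumed rate of incomplete dates. If misdating were concentrated among patients with long or short PFS, the shift could be larger and go either way. It would still lie well inside the interval for the median. PFS is a descriptive secondary endpoint in a study whose primary objective is safety. Only the estimate and its interval are at stake, and no hypothesis test is affected.

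**What to change.** In SAP 5.5.2:

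1. Define new anticancer therapy as therapy initiated after the first everolimus dose, so that a drug already ongoing does not count.
2. State that the first-dose-date imputation in 5.3.5 does not trigger row 5. Classify anticancer records with incomplete start dates from a medically reviewed listing before database lock.
3. Add anti-tumor surgery from the existing procedures and non-drug therapies CRF page, to match protocol 14.1.25, and state how antineoplastic radiotherapy is handled. Otherwise, declare the narrower definition in SAP Section 7.
4. Put the word or between the two bullets, as an editorial clarification.

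It would also help to say which of rows 2 and 5 prevails when both apply. A PFS run without censoring for Sandostatin LAR is optional.

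The cost is a few lines of SAP text and review of one medication and procedure listing. No CRF change and no compulsory extra analysis is needed.
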